**6.2.1.2 Secondary Analysis**

As a secondary analysis pairwise comparisons of the active dose groups with the placebo group will be performed without controlling the family-wise error rate, by calculating the 80% and 95% confidence intervals for the difference in primary efficacy variable between each active dose and placebo.

**6.2.1.3 Sensitivity Analysis**

**6.2.1.3.1 Treatment effect in FAS**

The primary analysis of the primary endpoint will be repeated on the FAS population defined in section 5.1.

### 6.2.1.3.2 COVID-19 related sensitivity analyses

1. The primary analysis will be repeated on the subpopulations of patients in PPS with and without an active COVID-19 infection (positive SARS-CoV-2 test by PCR / positive serology IgG test / an AE confirming COVID-19).
2. The same estimand as the primary efficacy estimand will be used with the modification that COVID-19 affected efficacy measurements will **not** be excluded, i.e. all available cough count data will be used for analysis. (The ICes a) and b) will be handled as described in Section 6.2.1.)
3. The analysis specified in 2. will be repeated on the FAS population.

### 6.2.1.3.3 Accounting for taste-related events

In order to account for confounding by taste disturbances, the primary analysis will be repeated on the subpopulations of patients in PPS with and without at least one treatment-emergent taste-related adverse event which cannot be attributed to a SARS-CoV-2 infection.

### 6.2.1.3.4 Accounting for respiratory tract infections

To account for the possible impact of respiratory tract infections on cough count, the primary analysis will be repeated on the subpopulations of patients in the PPS with and without a treatment-emergent AE belonging to the MedDRA HLTG "Respiratory tract infection", to the HLTG "Upper respiratory tract infections" or to the HLTG "Lower respiratory tract and lung infections".

### 6.2.1.3.5 Accounting for different lengths of measurements

Since average numbers of cough counts per hour will be used, different lengths of measurement will not be a problem. However, time of sleep / awake times may be a source of bias for the overall cough rate. Therefore, a sensitivity analysis will be performed with a weighted average of awake and asleep cough counts, i.e. weighting awake cough counts as if always coming from 16 hours and sleep cough times as if always coming from 8 hours. The following formula will be used:

$$\text{cough count}_{corr} = \frac{2}{3} \text{cough count}_{awake} + \frac{1}{3} \text{cough count}_{sleep}$$

Here, 'cough count' means the average cough count per hour (on the original scale), as in the above analyses. The analysis will follow the outline given above.

Further sensitivity analyses may be performed if the missing data patterns suggest further exploration.

## 6.2.2 Secondary Efficacy Endpoints

For each secondary endpoint the following three analyses will be provided:

1. The same estimand as the primary efficacy estimand will be used, in particular the analysis will be on PPS and COVID-19 affected efficacy measurements will be excluded. (The ICes a), b) and c) will be handled as described in Section 6.2.1.)
2. The analysis specified in 1. will be repeated on FAS.
3. The analysis specified in 1. will be repeated on PPS including also all data during and after potential COVID-19 infection (treatment policy strategy for ICE COVID-19 infection in c) and the ICes a) and b) will be handled as described in Section 6.2.1.)).

### 6.2.2.1 Secondary Efficacy Based on Cough Counts

- Percentage of participants with a  $\geq 30\%$  reduction from baseline in 24-hour cough count after 12 weeks of intervention

The proportion of participants meeting the responder threshold by intervention group will be compared across intervention groups using a Chi-square test.

Estimates and two-sided 80% and 95% confidence intervals will be provided for each treatment group and the treatment differences. Clopper Pearson confidence intervals will be calculated for each treatment group, while for treatment differences, due to the computational burden of exact unconditional confidence limits, Wald asymptotic confidence limits will be calculated.

The following two secondary efficacy endpoints will be analyzed with the same model as the primary efficacy endpoint.

- Change from baseline in 24-hour cough count after 2, 4, and 8 weeks of intervention.
- Change from baseline in awake cough frequency per hour after 2, 4, 8 and 12 weeks of intervention

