6.3 Measures to Minimize Bias: Randomization and Blinding

Participants will be identified by a unique participant number with 9 digits once the ICFs are signed. The first 5 digits will identify the country and study site, the last 4 digits are assigned to the participant of the specific site in increasing order.

Following the screening visit (Visit 1), all participants who meet all eligibility criteria will be centrally randomized in a 1:1:1:1 allocation ratio and stratified by region (Japan, Europe [Belgium, Czech Republic, France, Germany, Hungary, Italy, Netherlands, Poland, Slovakia, Spain, United Kingdom], ROW [Argentina, Australia, Canada, Russian Federation, Taiwan, Turkey, United States]) to receive either BAY 1817080 or placebo by using IWRS.

Once a randomization number has been assigned, it must not be re-assigned.

To accomplish randomization assignments, a computer-generated randomization list will be prepared by Randomization Management at the study sponsor. The randomization list is provided to the IWRS vendor. Before the study is initiated, the login information & directions for the IWRS will be provided to each site.

After randomization, participant, investigator and sponsor will be blinded for the intervention participant receives.

To maintain blinding, tablets containing BAY 1817080 and corresponding placebo are identical in appearance (size, color, shape). BAY 1817080 25 mg, 75 mg, and 150 mg, and matching placebos will be packaged in blisters labeled with a unique number. For regulatory reporting purposes, drug safety personnel of the sponsor are permitted to unblind individual cases. In compliance with applicable regulations, in the event of a suspected unexpected serious adverse reaction (SUSAR), the randomization code of the participant will usually be unblinded before reporting to the health authorities.

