9.4.3 Secondary Endpoints

The following table gives an overview of the secondary efficacy endpoints and outlines the key features of the planned analyses. Further details will be provided in the SAP.

Secondary Efficacy Based on Cough Counts
 
 Percentage of participants with a $\geq 30\%$ reduction from baseline in 24-hour cough count after 12 weeks of intervention (measured by cough recording digital wearable monitoring device) Change from baseline in 24-hour cough count after 2, 4, and 8 weeks of intervention (measured by cough recording digital wearable monitoring device) Change from baseline in awake cough frequency per hour after 2, 4, 8 and 12 weeks of intervention (measured by cough recording digital wearable monitoring device) 	
 The proportion of participants meeting the responder threshold will be compared across intervention groups using a Chi-square test. The secondary efficacy endpoints of cough count at different time points and awake cough count will be analyzed similar to the primary efficacy endpoints

HrQoL and PRO Associated Secondary Endpoints
 
 Change from baseline in cough related quality of life (measured by Leicester Cough Questionnaire) after 12 weeks of intervention Change from baseline in cough severity after 12 weeks of intervention (measured by Cough Severity Visual Analogue Scale (VAS)) Percentage of participants with a ≥ 30 scale units reduction from baseline after 12 weeks of intervention (measured by cough Severity VAS) Percentage of participants with a ≥ 1.3-point increase from baseline after 12 weeks of intervention (measured with Leicester Cough Questionnaire (LCQ) Total Score) 	
 The change from baseline will be analyzed by means of a mixed-model for repeated measurements (MMRM). This will be further detailed in the SAP The proportion of participants meeting VAS and LCQ responder thresholds by intervention group will be compared across intervention groups using a Chi-square test.

The secondary endpoint of TEAEs will be analyzed by descriptive statistics, such as frequency tables. All TEAEs will be tabulated according to the affected system organ class and preferred term, as coded by the Medical Dictionary for Regulatory Affairs (MedDRA). Further tables will be provided for serious and/or drug related TEAEs.

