### Analysis

In a first step the mean parameter estimates from an ANCOVA model and the corresponding covariance matrix are obtained. After this step, these two parameters will then be used during the rest of the MCP-Mod procedure.

For the estimation of  $\hat{\mu}$  and  $\hat{\mathcal{S}}$  in the initial stage SAS will be used. All MCP-Mod steps will be performed using the R “DoseFinding” package (version 0.9-17 or higher) [7].

Step 1: Estimation of  $\boldsymbol{\mu}$  and  $\mathbf{S}$  from ANCOVA model with covariate adjustment

An ANCOVA model, following adjustment for baseline cough count and region via the inclusion of covariates  $z$ , will be used to estimate the expected dose response  $\mu_{d_k}$  in each dose group  $k$ .

For participant  $i$  the response is then defined by:

$$Y_{ki} = \beta_0 + z_{1ki}\beta_1 + z_{2ki}\beta_2 + \mu_{d_k} + \varepsilon_{ki}$$

where  $\varepsilon_{ki} \sim \mathcal{N}(0, \sigma^2)$ ,  $k = 1, \dots, K$  and  $i = 1, \dots, n_k$ .

Let  $\hat{\boldsymbol{\mu}}$  denote the vector of estimated dose-response and let  $\mathbf{S}$  denote the variance-covariance of  $\hat{\boldsymbol{\mu}}$ . The estimate of the covariance matrix  $\mathbf{S}$  will be denoted by  $\hat{\mathbf{S}}$ .

Step 2: Detection of dose-response signal

For detecting an overall trend, or a dose-response signal, each of the  $M=4$  dose-response shapes in the candidate set will be tested, using a single contrast test.

For each model  $m$  in the candidate set

the null hypothesis  $H_{0m}: (\mathbf{c}_m)' \boldsymbol{\mu} = 0$

will be tested against

the respective 1-sided alternative hypothesis,  $H_{1m}: (\mathbf{c}_m)' \boldsymbol{\mu} > 0$

where  $\mathbf{c}_m = (c_{m1}, \dots, c_{mK})'$  is the optimal contrast vector representing model  $m$ . The contrast coefficients for the  $m$ -th model are chosen such that they maximize the power for a single candidate model shape

$$\boldsymbol{\mu}_m^0 = (\mu_{m1}^0, \dots, \mu_{mK}^0)' = (f_m^0(d_1, \boldsymbol{\theta}_m^0), \dots, f_m^0(d_K, \boldsymbol{\theta}_m^0))',$$

where  $f^0$  is the standardized version of the dose-response model

$$f(d, \boldsymbol{\theta}) = \theta_0 + \theta_1 f^0(d, \boldsymbol{\theta}^0).$$

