### 6.2.2.2 HRQoL and PRO Associated Secondary Endpoints

- Change from baseline in cough related quality of life (measured by Leicester Cough Questionnaire (LCQ)) after 12 weeks of intervention.

The scoring algorithm described in the LCQ manual [9] will be used.

The analysis will be the change in LCQ (each domain as well as the total score) from baseline to week 12 using mixed model repeated measures (MMRM). This method will assume that any missing data is Missing at Random (MAR).

The model statement is:

$$\Delta Y_{jtkl} = Y_{j0} + \mu_0 + trt_k + visit_t + (trt * visit)_{kt} + region_l + P_j + \varepsilon_{jtkl},$$

where  $\Delta Y_{jtkl}$  is the change from baseline to visit  $t$  for subject  $j$  within treatment group  $k$  and region  $l$ .

- $\mu_0$  is the intercept
  - $Y_{j0}$  is the baseline covariate effect
  - $trt_k$  is the fixed effect of treatment group  $k$
  - $visit_t$  is the fixed effect visit  $t$
  - $(trt*visit)_{kt}$  is the interaction fixed effect of treatment  $k$  by visit  $t$
  - $Region_l$  is the fixed effect of stratification factor
  - $P_j$  is the patient specific random effect.
- $P$  and  $\varepsilon_{tkl}$  will be assumed as normally distributed random variables.

Correlations among measurements taken on the same patient will be modelled with an unstructured covariance assumption. The degrees of freedom will be computed according to the method detailed by Kenward and Roger.

For each active dose  $d_k$  the null hypothesis:

$$H_{0k}: \mu_1 = \mu_k$$

will be tested against the alternative hypothesis

$$H_{1k}: \mu_1 \neq \mu_k$$

within this model.

Least square mean estimates, estimates of treatment differences and corresponding confidence intervals (CIs) will be computed. The least square mean estimates of treatment difference at week 12 are the main estimates of interest; however, differences at all other visits and overall treatment differences (averaged across all visits) will also be estimated as exploratory endpoints.

The core SAS-code to be used is the following (variable and dataset names are for illustration only and may be subject to change):

```
proc mixed data=adqslcq;
  class subject treat visit region;
  model change = base treat visit region treat*visit /ddfm=KR;
  repeated visit / subject=subject type=un group=treat;
  lsmeans treat*visit /cl diff;
  ODS OUTPUT TESTS3=TYPE3 LSMMeans=LSMEAN ESTIMATES=ESTIM;
run;
```

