### 6.2.2.3 Further secondary efficacy endpoints

- Percentage of participants with a  $\geq 30$  scale units reduction from baseline after 12 weeks of intervention (measured by Cough Severity VAS)
- Percentage of participants with a  $\geq 1.3$ - point increase from baseline after 12 weeks of intervention (measured with LCQ Total Score) [10]

The proportion of participants meeting Cough Severity VAS and LCQ Total Score responder thresholds by intervention group will be compared across intervention groups using a Chi-square test.

Point estimates and CIs for the probability of being a responder will be displayed by intervention group.

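### The VAS and LCQ responder endpoints have no planned difference from placebo with a confidence interval, and none of the three responder analyses uses baseline or region

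*SAP*

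**What the plan says.** **Responder tests.** Protocol 9.4.3 says of the cough-count responder: "The proportion of participants meeting the responder threshold will be compared across intervention groups using a Chi-square test". It plans a chi-square for the VAS and LCQ responders too. The SAP repeats this in 6.2.2.1 ("The proportion of participants meeting the responder threshold by intervention group will be compared across intervention groups using a Chi-square test") and in 6.2.2.3 ("The proportion of participants meeting Cough Severity VAS and LCQ Total Score responder thresholds by intervention group will be compared", again by chi-square). No covariate, stratification or degrees of freedom is named.

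**Responder estimates.** For the cough-count responder, SAP 6.2.2.1 continues: "Estimates and two-sided 80% and 95% confidence intervals will be provided for each treatment group and the treatment differences". The intervals are Clopper-Pearson by group and unadjusted Wald for the differences. For VAS and LCQ, SAP 6.2.2.3 has only this: "Point estimates and CIs for the probability of being a responder will be displayed by intervention group". The exploratory ≥50% and ≥70% cough responders in SAP 6.2.3.1 are handled as in 6.2.2.3.

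**Continuous versions.** Protocol 6.3 has participants "centrally randomized in a 1:1:1:1 allocation ratio and stratified by region". The primary analysis in SAP 6.2.1.1 is described as "An ANCOVA model, following adjustment for baseline cough count and region via the inclusion of covariates". The LCQ model in SAP 6.2.2.2 is "model change = base treat visit region treat*visit /ddfm=KR", and the same model is used for VAS. It yields least-squares mean differences with intervals.

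**The concern.** SAP 6.2.1.1 (Step 3) bases the final dose choice on primary, secondary and other efficacy results together with safety. That choice needs the size and uncertainty of each dose's effect against placebo. On the safety side, SAP 6.4.1.1 plans odds ratios with 80% and 95% intervals for taste-related events. For the VAS and LCQ responders, the plan gives separate group proportions and an across-group p-value. If the chi-square is one test on four groups, that p-value does not depend on which arm did best. The crude difference can be had by subtraction, but its interval is not planned.

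No other section fills the gap. SAP 4.1 sets only interval coverage levels, 6.2.2 repeats the analyses on the FAS and with COVID-19-affected data included, and 6.2.4 repeats them in subgroups.

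The second part concerns consistency. The same three measures are adjusted for baseline and region when analysed as continuous, and for neither when dichotomised. No reason is given.

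**Working it through.** **Inputs.** From Protocol 9.2 and 9.4.2: placebo change -0.19 on the log scale, SD 0.8, 50 evaluable per arm, and the Emax1 curve -0.19 - 0.42·d/(30 + d). The responder cut-off is log 0.7 = -0.357. The documents state no rate or power for any responder endpoint. The one related planning figure, at least 85% power for the primary test, reproduces from these inputs to rounding: 84.6% to 91.3% across the four candidate curves.

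**Implied cough-count responder rates.** P(responder) = Φ((-0.357 - μ_d)/0.8).

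| Arm | μ_d | Rate | Of 50, rounded |
|---|---|---|---|
| Placebo | -0.190 | 0.417 | 21 |
| 25 mg | -0.381 | 0.512 | 26 |
| 75 mg | -0.490 | 0.566 | 28 |
| 150 mg | -0.540 | 0.591 | 30 |

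**What a global chi-square reports.** The total is 105 of 200, so each arm expects 26.25 responders and 23.75 non-responders. The squared deviations sum to 5.25² + 0.25² + 1.75² + 3.75² = 44.75. Then χ² = 44.75 × (1/26.25 + 1/23.75) = 3.59, and p = 0.31 on 3 df. With the arms in reverse order, so that placebo is best, χ² and p are identical.

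**What a difference with an interval reports.** For 150 mg versus placebo, 0.60 - 0.42 = 0.18. SE = √(0.60·0.40/50 + 0.42·0.58/50) = 0.0983.
- 80%: 0.18 ± 1.282 × 0.0983, or +5 to +31 points.
- 95%: 0.18 ± 1.960 × 0.0983, or -1 to +37 points.

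This is the output that 6.2.2.1 plans for cough count and 6.2.2.3 omits for VAS and LCQ.

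**VAS and LCQ.** No rates are given, so I assume 20-70% in both arms compared. At p = 0.2, SE = √(2·0.2·0.8/50) = 0.080, with half-widths of 10 points (80%) and 16 points (95%). At p = 0.5, SE = 0.100, with half-widths of 13 and 20 points. Intermediate cases lie between.

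**Value of adjustment, cough-count responder.** I simulated 4,000 trials per correlation: Emax1, 50 per arm, change SD 0.8, assumed region shares of 15/55/30% with no region effect. The model was logistic with treatment, region and baseline, and gave a standardised risk difference for 150 mg versus placebo. The baseline-to-change correlation is not in the documents, so a range is shown.

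| Correlation | SD ratio, adjusted/unadjusted | 95% half-width, from 19.3 points |
|---|---|---|
| 0 | 1.007 | 19.4 |
| -0.2 | 0.996 | 19.2 |
| -0.4 | 0.958 | 18.5 |
| -0.5 | 0.927 | 17.9 |

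Another simulation gave 0.92 at -0.5, hence a stated gain of 7-8% there.

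**The case against.** The strongest reply is that little is lost. The chi-square is valid under stratified randomisation. The VAS and LCQ responders dichotomise data that SAP 6.2.2.2 already compares dose by dose with placebo, adjusted and with intervals. Unadjusted analysis is also the SAP's uniform practice for binary outcomes: even the taste-event logistic model has treatment as its only factor. Adjusted logistic models break down in small subgroups. In simulation, separation or non-convergence occurred in about 22% of subgroups with 8 per arm and 10% with 10 per arm at the planning rates, and in 46% and 30% at response rates of 20-40%.

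Much of this stands. The taste model supports the reporting point but not the adjustment point. The subgroup argument is sound, so adjustment should be confined to the overall analyses. The continuous results do inform the dose choice.

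They do not replace the responder difference, however. The sponsor made the responder proportions secondary endpoints in their own right and planned this very interval for one of the three. A reader might infer from the omission that the dose decision has no placebo-controlled VAS or LCQ evidence; 6.2.2.2 shows that it has.

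**Conclusion.** The point holds as a gap in estimation and reporting, with a smaller point about precision.

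- **Reporting.** Two of the three responder secondary endpoints lack a planned dose-versus-placebo difference with an interval. The third has one, and no reason for the difference is given. This part rests on the text alone.
- **Precision.** The gain from adjustment runs from about 7-8% narrower (correlation -0.5), through about 4% (-0.4), to unchanged or under 1% wider (0). It rests on the planning assumptions and an unstated correlation, and is calculated for cough count only.

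Three stronger readings are tempting, and the documents do not support them:
- *The unadjusted test is invalid or inflates type I error.* It is valid, and the primary MCP-Mod test does not depend on it.
- *Ignoring region or baseline costs material power.* No region effect or correlation is given, and the no-gain case is within the plausible range. Reporting pairwise differences does not by itself add power either: at two-sided 0.05, top dose versus placebo has about 40-41% on the planning curves, against 32-41% for a 3-df chi-square.
- *A dose-ordered contrast should replace the chi-square.* Candidate shapes are specified only for log cough count, the planned LCQ and VAS comparisons are themselves unordered, and such a contrast loses some power if response falls at the top dose.

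**What to change.** 1. In SAP 6.2.2.3, and for consistency in 6.2.3.1, add the risk difference of each dose versus placebo with 80% and 95% intervals, using the method already set in 6.2.2.1. State in all three places whether the chi-square is one 3-df test or a set of pairwise tests.
2. For the overall analyses of the three responder secondary endpoints, also report the risk difference versus placebo adjusted for region and the matching baseline (log hourly cough count, VAS or LCQ total score). A standardised risk difference from a logistic model would serve. Label its p-values nominal. Specify that the unadjusted difference is used if the model does not converge or shows separation.
3. Keep subgroup responder analyses unadjusted. The five-participant minimum in SAP 6.2.4 covers only the primary analysis and the MMRM.

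Item 1 is a few sentences and reuses existing methods. Item 2 takes modest programming, run for each of the three analyses per endpoint in SAP 6.2.2, and may cost under 1% in precision if baseline is not prognostic. Neither needs new data.

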9.2 Sample Size Determination

Sample size calculations were performed for establishing evidence of a drug effect across the doses, that is, detecting a statistically significant dose response signal for the primary efficacy outcome in this study using the MCP-Mod approach.

Treatment effects are here presented on the log scale of average hourly counts, measured over 24 hours (see Section 9.4.2 for calculation details and interpretation).

Assuming a true change in cough count under placebo after 12 weeks of -0.19 (17% reduction), a maximum cough count change of -0.35 for BAY 1817080 over placebo (30%

reduction relative to placebo), a common standard deviation of 0.8, a set of plausible dose-response shapes including Emax and sigmoidal Emax models (chosen based on BAY 1817080 effects in Study 18184 combined with literature review), random allocation of participants to dose groups according to a 1:1:1:1 ratio, a sample size of 50 participants per dose groups will have at least 85% power to demonstrate a dose-response relationship, using a one-sided test at a type I error rate of $\alpha=0.10$. Approximately 236 participants will be randomized to achieve 200 evaluable participants for an estimated total of 50 evaluable participants per intervention group. The number of participants to be randomized might be increased if more participants than expected become unevaluable due to COVID-19 related circumstances, to maintain the goal of 50 evaluable participants per intervention group.

With this sample size, the dose-response curve is expected to be estimated with 80% confidence bands of half-widths of 0.14 to 0.16, depending on the underlying dose-response relationship.

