### 6.2.1.1 Primary Analysis

For the primary efficacy variable, it is planned to perform a test for a dose-response signal in the study population, under the assumption of a monotone dose-response relationship in the dose range considered. The MCP-Mod method [5] combining *multiple comparison procedures* principles with *modeling techniques* (MCP-Mod) will be used for the primary analysis of the primary efficacy variable. This method allows the flexibility of modeling for dose estimation, while preserving the robustness to model misspecification associated with MCP procedures. More specifically, it is planned to use a generalization of the original MCP-Mod method which allows to perform dose-response testing and modeling in conjunction with the response variable being described by a parametric model [6]. The key idea of this generalization is to decouple the dose-response model from the expected response so that the dose response can be characterized using a suitable parameter in the probability distribution of the response.

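### The responder endpoints are tested only with an omnibus chi-square that ignores dose order; adding an ordered-dose test would gain about 6 to 15 points of power for the 24-hour cough responder at a two-sided 5% level

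*SAP*

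**What the plan says.** For the 30% cough responder, SAP 6.2.2.1 states that the proportion "will be compared across intervention groups using a Chi-square test". SAP 6.2.2.3 applies the same method to the other two secondary responders: the VAS and LCQ "responder thresholds by intervention group will be compared across intervention groups using a Chi-square test". SAP 6.2.3.1 repeats it for the exploratory 50% and 70% cough responders. Protocol 9.4.3 also names the chi-square for the three secondary endpoints. None of these sections names a trend or ordered-dose test, and none gives degrees of freedom, a significance level or sidedness.

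The accompanying estimates differ by endpoint. For the 30% cough responder, SAP 6.2.2.1 adds: "Estimates and two-sided 80% and 95% confidence intervals will be provided for each treatment group and the treatment differences". For VAS and LCQ, SAP 6.2.2.3 says only: "Point estimates and CIs for the probability of being a responder will be displayed by intervention group".

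The primary variable is treated differently. SAP 6.2.1.1 tests it for a dose-response signal "under the assumption of a monotone dose-response relationship in the dose range considered", with four candidate curves and one-sided contrasts. SAP 6.2.2.1 carries that model over to the earlier cough time points and to awake cough frequency.

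**The concern.** The trial exists to find a dose. The week-12 24-hour cough count is tested with dose order when it is kept continuous, and without it once it is cut at a 30% reduction. The SAP gives no reason for the change.

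A chi-square over four arms spends 3 degrees of freedom on any difference at all. It gives the same result if the dose labels are shuffled, so a significant p-value does not show that response rises with dose. If the truth resembles the plan's candidate curves, most of the signal lies along one ordered direction, and the omnibus test dilutes it.

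What is at stake is supporting evidence. SAP 6.2.1.1 says that the target dose will be chosen from the primary, secondary and other efficacy analyses together with safety, and the responder results are part of that picture.

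**Working it through.** **Inputs.** Protocol 9.2 gives 50 evaluable per arm, equal allocation, a placebo log change of -0.19, "a maximum cough count change of -0.35 for BAY 1817080 over placebo", and SD 0.8. The four curves are in Protocol Table 9–1 and SAP Table 6–1, at doses 0, 25, 75 and 150 mg BID. Three things are assumed here because the SAP does not state them: a two-sided 5% level, 3 df (four groups by two outcomes), and the scores for any trend test.

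**1. Reproduce the plan's own power.** Protocol 9.2 claims at least 85% for the primary test, "using a one-sided test at a type I error rate of" 0.10. Optimal contrasts for the four curves, 196 df and a simulated critical value of 1.485 give 84.4, 84.9, 88.9 and 91.2% (Emax 1, Emax 2, sigmoidal 1, sigmoidal 2). The lowest is 0.6 points under the claim, so the inputs are read as intended.

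**2. Responder rates.** A reduction of at least 30% means a log change of at most ln 0.7 = -0.357. The rate at dose d is therefore Φ((ln 0.7 - mean at d)/0.8).
- Placebo: Φ((-0.357 + 0.19)/0.8) = Φ(-0.208) = 41.7%.
- 150 mg, Emax 1: mean = -0.19 - 0.42 × 150/180 = -0.54, so Φ(0.229) = 59.1%.
- Across the four curves: 42.0 to 51.2% at 25 mg, 54.8 to 58.0% at 75 mg, about 59% at 150 mg.

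**3. Hand check for Emax 1.** The rates are 0.4175, 0.5121, 0.5662 and 0.5906. Their mean is 0.5216, and the variance term is 0.5216 × 0.4784 = 0.2495. The deviations from the mean are -0.1041, -0.0095, 0.0446 and 0.0690.
- Chi-square: non-centrality = 50 × (sum of squared deviations, 0.0177)/0.2495 = 3.54. On 3 df at 5% this gives 32% power.
- Trend, scores -1.5, -0.5, 0.5, 1.5: non-centrality = 50 × 0.2867²/(5 × 0.2495) = 3.30. Power is Φ(√3.30 - 1.96) = Φ(-0.145) = 44%.
- Trend, mg scores centred at 62.5: non-centrality = 50 × 13.46²/(13,125 × 0.2495) = 2.77. Power is Φ(1.663 - 1.96) = 38%.

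With equal spacing, the trend test keeps 3.30 of the 3.54 units of signal and pays for one degree of freedom instead of three.

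**4. Simulated power.** 200,000 trials of 4 × 50 per curve. The chi-square and trend tests are at two-sided 5%. The maximum-contrast test is at one-sided 2.5%, which is the directional half of that level. Gains are taken before rounding.

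| Test | Emax 1 | Emax 2 | Sigmoidal 1 | Sigmoidal 2 |
|---|---|---|---|---|
| Chi-square, 3 df | 32.3% | 32.2% | 36.8% | 41.6% |
| Cochran-Armitage, equal spacing | 45.4% | 47.0% | 50.6% | 54.5% |
| Gain, points | 13.1 | 14.9 | 13.8 | 12.8 |
| Maximum contrast, plan's curves | 44.8% | 45.7% | 51.5% | 55.7% |
| Gain, points | 12.5 | 13.5 | 14.7 | 14.1 |
| Cochran-Armitage, mg scores | 38.4% | 41.6% | 44.3% | 53.7% |
| Gain, points | 6.2 | 9.4 | 7.5 | 12.0 |

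**5. Sensitivity, equal spacing.** At a shared two-sided 10% level the gain is 11.7 to 14.9 points. With all 236 randomised participants counted (236/4 = 59 per arm), at 5%, it is 12.3 to 15.5 points.

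**6. VAS and LCQ.** The documents give no responder rates and no SDs for these endpoints, so the calculation cannot be repeated for them.

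**The case against.** The strongest reply is that these are supportive tests. The plan claims no power for them, and the evidence on dose order is already supplied by the primary analysis of the same cough recordings. No responder p-value gates the choice of dose. That stands, and it limits the point to one of efficiency.

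Four stronger readings are tempting, and the documents do not support them.
- **Direction is never reported.** For the 30% cough responder it is, because SAP 6.2.2.1 plans intervals for the treatment differences. Only the p-value is directionless. Those intervals are still not a test of dose trend, and for VAS and LCQ only per-group intervals are listed.
- **The loss is 13 to 15 points for all responder endpoints.** That range needs a two-sided 5% level with equal spacing or the plan's contrasts, and it covers the cough responder alone. With mg scores the gain is 6 to 12 points.
- **At the trial's 10% level the gap is 44 to 54% against 71 to 80%.** This sets the non-directional chi-square beside a one-sided contrast test, so it mixes dose order with sidedness. The like-for-like 10% figure is in step 5 of the working.
- **The plan assumes monotonicity throughout.** SAP 6.2.1.1 assumes it for the primary variable. The continuous PRO changes in SAP 6.2.2.2 are analysed with treatment as an unordered factor and two-sided pairwise hypotheses.

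**Conclusion.** The concern holds as a cheap improvement. The only test planned for the responder endpoints disregards dose order in a dose-finding trial, and an ordered test on the 30% cough responder had more power under every candidate curve. At a two-sided 5% level the gain is roughly 6 to 15 points, depending on the scores. Put another way, the chi-square would miss the effect that the plan assumes in about 58 to 68% of trials.

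The size rests on 50 per arm, SD 0.8, normally distributed log changes, one of the four candidate curves being true, and a level that the SAP leaves unstated. No figure in the plan is wrong. For VAS and LCQ the argument about dose order applies, but the gain is unknown.

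**What to change.** Before unblinding, pre-specify an ordered-dose test for the responder endpoints in SAP 6.2.2.1, 6.2.2.3 and 6.2.3.1. Two options fit the plan:
- the same four candidate contrasts applied on the logit scale, using the generalised MCP-Mod method already adopted in SAP 6.2.1.1; or
- a Cochran-Armitage test with stated scores. In the simulations, equally spaced scores did at least as well as mg scores under every candidate curve at two-sided 5%, although the two were nearly level under sigmoidal 2.

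State the level and sidedness. Keep the chi-square alongside, because Protocol 9.4.3 specifies it, and record the change from that section in SAP section 7.

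The cost is a few sentences and a short program. The statistical price is less power against non-monotone patterns. The plan assumes these away only for the primary variable, which is a further reason to retain the chi-square for VAS and LCQ.
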